## **1.0 PROTOCOL SUMMARY AND/OR SCHEMA**

Patients undergoing ambulatory cancer surgery at Josie Robertson Surgery Center (JRSC) at MSKCC will be eligible to participate in a randomized controlled trial comparing two different methods of symptom monitoring while recovering from ambulatory surgery. The study will evaluate the differences in patient-centered outcomes and experiences between Team Monitoring (symptom monitoring by the clinical team, with nursing outreach if symptoms exceed normal limits) and Enhanced Feedback (real-time feedback to patients about expected symptom severity, with nursing outreach if indicated) in response to the patients' daily symptom reporting.

A total of 2,750 adult patients and 1,375 caregivers will be recruited for this study at the JRSC. All potential participants will be informed of their rights as a volunteer in a research study. Patient disease types will include breast, urologic, gynecologic, and head and neck cancers, as well as benign diseases. Randomization will take place through the Clinical Research Database (CRDB). Patients will complete a symptom assessment (Recovery Tracker) for the first 10 days after surgery. Over the following 20 days, patients can tailor the survey to their needs by choosing when they complete the survey. Between days 11-30, patients can report symptoms on any day. By leaving the survey open after day 10, patients who develop new or worsening symptoms will have the ability to report these symptoms electronically whenever they wish. Conversely, patients not experiencing any symptoms will not be burdened by additional surveys. Outcomes will be measured for up to 60 days and will include patient anxiety, patient engagement, caregiver burden, urgent care visits, detection of adverse events, and nursing interventions.

The proposed study will not evaluate any investigational agents or methods that are not considered standard of care for this patient population. Therefore, there are minimal risks to the patient population. In both groups, if a patient reports severe symptoms, they are instructed to immediately contact their physician's office or seek medical attention, as is the current standard of care. Alternatives to participation in this study include the standard of care, which includes completing the Recovery Tracker (the Team Monitoring arm of the study), or not completing any surveys at all.

## 2.0 OBJECTIVES AND SCIENTIFIC AIMS

We will perform a prospective, two-armed, randomized controlled trial of postoperative daily symptom reporting among patients undergoing ambulatory cancer surgery, to determine which of two approaches to management of patient-reported symptom data is most effective from a patient and caregiver perspective: (1) symptom monitoring by the clinical team, with nursing outreach if symptoms exceed normal limits (**Team Monitoring**), or (2) feedback to patients about expected symptom severity, with patient-activated care as needed (**Enhanced Feedback**). For symptom self-reporting, we will use a 20-question survey that includes 11 items from a validated instrument, the Patient Reported Outcomes Common Terminology Criteria for Adverse Events (PRO-CTCAE), three additional surgical symptom questions, and two questions about seeking urgent care or a doctor. The information provided to patients in the **Enhanced Feedback** group will be procedure-specific and based on continuously updated PRO-CTCAE data from previous patients who have completed PRO-CTCAE data. **We hypothesize that Enhanced Feedback about expected symptom severity will be more effective than Team Monitoring in improving patient-centered outcomes (SA1) and the patient/caregiver experience (SA2).**

**Specific Aim 1 (SA1):** To compare the effectiveness of **Team Monitoring** and **Enhanced Feedback** with regard to patient-centered outcomes, including:

- SA1a – urgent care, emergency department visits, and readmissions up to 30 days
- SA1b – symptom-triggered interventions.

**Specific Aim 2 (SA2):** To compare the impact of **Team Monitoring** and **Enhanced Feedback** on the health care experience of patients and their caregivers, including:

- SA2a – patient engagement
- SA2b – patient anxiety
- SA2c – caregiver burden

### **3.0 BACKGROUND AND RATIONALE**

More than 1.5 million people were diagnosed with cancer in the US in 2015; most underwent surgery as a component of their treatment. With health care cost constraints and recent technical innovations, increasing numbers of these surgeries are performed as ambulatory procedures. This new model of short-stay surgery adds new complexities to the delivery of high-quality, patient-centered care. Although there are many advantages to shorter hospital stays, there is also an increased burden on patients and their caregivers. Postoperative symptoms, such as pain and nausea, are common and represent a major source of morbidity and distress for patients. After discharge, patients may have difficulty distinguishing normal and expected symptoms from potentially dangerous ones. This may lead to unnecessary worry and health care use for normal symptoms, or worse, to unnecessary suffering and serious adverse events, when worrisome symptoms are unrecognized and neglected.

There is abundant evidence that patient self-reporting of symptoms improves quality of care, and thus patients are increasingly being asked to provide this information as a component of routine clinical care. A key knowledge gap in patient-centered care, however, is that we don't know the most effective way to monitor and manage such data. To address this gap, we will conduct a randomized clinical trial among a diverse patient population, using an established informatics platform and well-validated symptom assessment questions developed by the National Cancer Institute PRO-CTCAE. We will compare two approaches, each of which has demonstrated effectiveness: (1) Team Monitoring—symptom monitoring by the clinical team, with nursing outreach if symptoms exceed normal limits, and (2) Enhanced Feedback—real-time feedback to patients about expected symptom severity, with patient-activated care as needed. The information provided to patients in the Enhanced Feedback group will be procedure specific and based on continuously updated PRO-CTCAE data from previous patients. We hypothesize that Enhanced Feedback about expected symptom severity will be more effective than Team Monitoring because patients will feel greater self-efficacy and engagement in their care. We will evaluate the following outcomes: Aim 1—urgent care and emergency department visits and symptom-triggered interventions; Aim 2—patient engagement, patient anxiety, and caregiver burden (Aim 2), as measured by validated patient-reported outcomes (PROs) measures and qualitative interviews.

#### **Impact on the health of individuals and populations**

Ambulatory surgery is increasingly common, and it places new burdens on patients and caregivers. Enabled by technical innovations in surgery and anesthesiology, and driven by pressures to reduce costs, ambulatory procedures account for increasing proportion of surgeries. In the US in 2015, patients underwent approximately 50 million short-stay (23-

hour) or ambulatory surgery procedures. Although this approach may help to contain health care costs, it places new burdens on patients and caregivers. Patients no longer have the physical and psychological support of 24-hour care by nurses and allied professionals, nor do they receive daily visits by their surgeon. Instead, they are expected to manage the recovery process largely at home, with access to their clinical team only when they perceive that a complication may be occurring. In addition, their caregivers are asked to provide support without the benefit of knowledge or clear expectations about what symptoms are normal during postoperative recovery. Focus group and survey data from our institution suggest that caregivers experience tremendous burden, which significantly affects the primary caregiver's health, psychological well-being, and schedule.

Cancer patients undergoing surgery are especially vulnerable to this new model of care. The lifetime risk of developing cancer is approximately 40%, and most patients undergo surgery as part of their treatment. Major procedures, such as mastectomies, prostatectomies, and hysterectomies, are now being performed as ambulatory procedures, and patients often leave the surgical center while still experiencing symptoms. Patients undergoing cancer surgery are particularly at risk in this new model of care, as they are often preoperatively compromised both physically and psychologically by their diagnoses and neoadjuvant treatments. From a psychological perspective, these patients and their caregivers are often still struggling to adjust to a new cancer diagnosis at the time of surgery; they may thus feel heightened anxiety, which may overwhelm coping skills.

### **Potential benefits and relevance for patients**

Patients experience postoperative symptoms at home but may not be able to distinguish expected from worrisome symptoms. Following ambulatory cancer surgery, symptoms are very common and are a source of considerable patient distress. Patients are expected to self-interpret symptoms and distinguish expected postoperative symptoms from those of concern—which is especially difficult when patients and caregivers have no way to know what is normal and expected. There is strong evidence that physicians may underestimate patient symptoms, and patients are often reluctant to report them. This may lead to unnecessary suffering and serious adverse events when worrisome symptoms are unrecognized and neglected. Symptom self-reporting can improve safety by identifying problems that might have otherwise been unrecognized and can facilitate more efficient care before complications progress. Symptom self-reporting with feedback about expected symptom severity may also decrease anxiety and inefficient health care use.

### **Gaps in evidence and national interest**

Our study addresses a high-priority knowledge gap. We do not yet know what is the most effective method to monitor and manage patient symptom data after ambulatory cancer surgery. Monitoring of symptoms, with outreach by the clinical team when severity exceeds the expected range, may identify problems at an earlier stage, to avoid or minimize adverse events, but it is resource intensive. Alternatively, providing patients with feedback about expected symptom severity and allowing them to activate care as needed may allow for the identification of adverse events before they progress, while also decreasing patient anxiety and unplanned care, such as unnecessary visits to the

emergency department. In addition, patient focus groups have reported to us that feedback about expected symptoms increases patient engagement in their care and gives them a sense of empowerment.

A systematic review of randomized controlled trials that evaluated electronic reporting of symptoms confirmed that this is a major limitation in our knowledge. Although progress has been made to better understand how symptom data might be best incorporated into clinical care among nonsurgical ambulatory patients, little work has been done among patients having surgery. Notably, none of the 32 randomized controlled trials identified in this review evaluated symptom assessment in surgical patients. Furthermore, dual PIs [name] and [name] organized an Agency for Healthcare Research and Quality–funded conference on PROs in surgery in January 2015. This meeting, cohosted by the American College of Surgeons, engaged a broad group of surgeons, patient advocates, quality of life researchers, and health informatics experts. At this meeting, a Delphi survey was conducted, which identified optimal evaluation and reporting of patient-reported symptoms for clinical care as a top research priority. Our study thus provides a unique opportunity to address a critical evidence gap of utmost importance to patients and the surgical stakeholder community.

Our study addresses an evidence gap that is directly in line with the aims of the Institute of Medicine. By determining which of these two approaches to monitoring and managing surgical patients' symptoms is the most effective, we will promote care that is timely, equitable, efficient, and coordinated. We may also improve patient safety and outcomes. Through earlier detection of worrisome symptoms, we can prevent serious adverse events. By communicating normative data on symptom burden to patients, reassuring them when they are on track and encouraging them to seek appropriate resources if problems develop, we can foster effective, patient-centered care.

### **The potential of this study to be adopted into clinical practice and improve delivery of care**

Collection of PRO data in routine care is rapidly expanding, with data being collected in many different clinical scenarios and used in many different ways. We don't, however, know how to optimally use this information to maximally improve patient care. We hypothesize here that unnecessary emergency department visits and serious adverse events can be reduced if patients are provided with feedback about expected symptom severity and that this will be more effective than standard PRO monitoring by the clinical team. If we are correct, Enhanced Feedback, with its resulting patient-activated care, could easily be adopted by other facilities and could benefit large numbers of patients undergoing cancer and noncancer surgery alike, in both large- and small-volume centers. A system that features feedback based on normative data would be less costly than clinical team monitoring and would require less infrastructure and personnel for monitoring and follow-up phone calls. These savings—along with reduced complications, readmissions, and emergency department visits and improved outcomes and patient experience—would offset upfront costs for information technology infrastructure and implementation. We thus anticipate that our findings will be rapidly adopted in a variety of ambulatory surgery environments, including smaller centers

that do not have the personnel resources necessary to provide intensive monitoring of patient symptoms.

Although symptoms may differ by condition and treatment, the key lessons learned in our study will support the implementation of wider strategies for population health management for any treatment with burdensome side effects or symptoms. We expect that these tools will be highly relevant in designing coordinated care models that target improved health care value, such as the Oncology Care Model and the Perioperative Surgical Home. Thus, we believe that the knowledge gained here will be highly generalizable and will have a broad impact on surgical care overall.

There is abundant and broad evidence that routine collection of PROs and symptoms improves quality of care. Such studies have confirmed that PRO data can improve communication with the clinical team, symptom control, quality of life, and patient satisfaction. As an example, study consultants [name] and [name] reported on a large randomized trial that compared routine collection of PROs with usual care during chemotherapy. In this study, nurses received and responded to email alerts when symptoms exceeded expected values or were noted to be worsening. Among patients who received the PROs intervention, quality of life improved (34% v 18%), and these patients were less likely to be seen in the emergency department (34% v 41%;  $P = 0.02$ ) or hospitalized (45% v 49%;  $P = 0.08$ ). This study and others provide a substantial foundation for the design of our study and the selection of our outcome measures. PROs measurement is rapidly becoming a standard of care, and our study represents an essential step to ensuring that patient-reported data is optimally integrated into health care systems to provide the greatest benefit to surgical patients and caregivers.

[figure not shown]
Our team has tremendous experience collecting and monitoring PROs data in routine clinical care. Using an informatics platform developed by our study team ([name], [name], [name], [name], [name], and [name]), patients complete validated PRO measures at regular postoperative intervals at MSKCC, and this information is used during clinical visits to improve patient-centered care. In the MSKCC Department of Surgery, more than 50,000 patients have completed such PRO assessments in routine clinical care. For example, on the MSKCC Breast Surgery Service, 8000 patients have participated, completing more than 22,000 BREAST-Q surveys (a PRO measure developed by study dual PI [name]). Nurses use this information to monitor postoperative pain and physical function and to provide referrals for physical therapy and pain management as needed. On the Urology Service, more than 6,000 patients have participated, using validated urology-specific PRO instruments.

## 4.1 OVERVIEW OF STUDY DESIGN/INTERVENTION

### 4.2 Design

Our study model is predicated on the hypothesis that daily symptom assessment with normative data (**Enhanced Feedback**) will increase patients' self-efficacy and their confidence that they can manage their symptoms in the recovery period. Without

information and risk awareness, patients may delay seeking care, with severe consequences, and/or they may experience unnecessary anxiety and fail to cope with their health conditions. The normative data provided by the symptom monitoring modules in the patient portal will empower our patients, resulting in increased self-efficacy, and will help the patients to form realistic expectations, which has been shown to be a predictor of decreased symptoms and better physical function. On the basis of this model, we predict that patients may avoid unnecessary emergency department visits by better understanding expected symptoms and by achieving more efficient and effective communication with their health care team. The aims our study and the outcomes measures selected reflect this model.

### Methodological approach

The study is a parallel group trial, with 1:1 procedure-stratified randomization between the Team Monitoring and Enhanced Feedback arms. The two groups will differ by how their self-reported symptom information is handled: Enhanced Feedback (system displays the patient's self-reported symptom data alongside expected norms for that procedure, and patient initiates care escalation) vs. Team Monitoring (the patient completes self-reported symptom assessment as per standard care at MSKCC; the clinical team contacts the patient if symptoms are above expected levels or appear to be worsening). Note: When patients report severe symptoms in either group, the care team will receive an alert and patients will also be instructed to immediately contact the clinical team. (Alerts to the clinical team can only be monitored during business hours, so all patients must seek care after hours in the current standard care fashion.) Our study design follows CONSORT and PCORI standards, including patient engagement, research methods, data integrity and

analysis (including stratification by surgical procedure), handling of missing data, and heterogeneity of treatment effect.

**Primary outcome:** The primary outcome for Aim 1, emergency department visits up to 30 days after ambulatory cancer surgery, is important to patients because emergency department visits are time-consuming and may increase anxiety and caregiver burden. It is relevant to health care systems and clinicians because such visits are inefficient and costly and may erode trust between the patient and provider.

**Secondary outcomes:**

**SA1:** We will evaluate symptom-triggered interventions (nursing follow-up calls, unplanned clinic visits and phone referral to clinic, pain management referrals, and adverse event detection) and rates of adverse events up to 30 days after ambulatory cancer surgery. We will also evaluate the number of readmissions up to 30 days. Adverse events will be defined according to the nomenclature established in the MSKCC Surgical Secondary Events Grading System.

**SA2:** We will evaluate patient engagement, patient anxiety, and caregiver burden with the experience of care using validated PROs measures and qualitative interviews.

- Patient engagement will be evaluated preoperatively and at 2 weeks and 2 months postoperatively using the Patient Activation Measure (description below).
- Patient anxiety will be measured on a daily basis for 10 days following surgery using three PRO-CTCAE Anxiety questions.
- Caregiver burden will be evaluated at 2 weeks and 2 months postoperatively among consenting caregivers using the Caregiver Reaction Assessment (description below). Each participating patient will be asked to identify a caregiver, who will then be invited to participate.
- Patient engagement and caregiver burden will also be evaluated using qualitative interviews, with a sample of each of the randomized cohorts, as described below.

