#### **Cohort 1: Team Monitoring**

Team Monitoring is the current standard of care for patients at JRSC. In this cohort, the electronic system will provide advanced informatics support for push notifications to the care team based on the severity of the symptoms reported. This platform promotes early detection and intervention. The care team is alerted when patients experience symptoms out of the expected range or if symptoms are worsening. Nurses receive secure message notifications and will contact the patient by phone depending on symptom severity. If a patient responds with a moderate-severe answer, the office team gets an alert and calls

the patient during business hours. Although nurses endeavor to call patients within 24 hours, this may not occur if symptoms are reported on weekends or holidays. If the patient reports very severe symptoms, they get a bold red alert instructing them to call the office (or call team after hours) immediately or seek medical attention. The actual response thresholds (i.e., when to give which alert) for each question are set individually and have been refined based on feedback from the office practice nurses. The workflow associated with Team Monitoring has been vetted by all teams at JRSC and has been operationalized for urology, breast, and gynecologic oncology patients.

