## **Cohort 2: Enhanced Feedback**

In this cohort, the electronic system will provide tailored normative data visualizations that offer context and education to patients regarding expected symptom severity. The information provided to patients in the Enhanced Feedback group will be procedure specific and based on continuously updated PRO-CTCAE data from previous patients. Patients are thus able to see their own recovery trajectory relative to that of patients who have undergone the same procedure. Care is patient-activated in that patients will use the information about expected symptoms to decide whether they should call the care team (e.g., if they are experiencing symptoms that are more severe or more prolonged than expected). If a patient reports severe symptoms, they are instructed to immediately contact their physician's office or seek medical attention. In addition, when patients in the Enhanced Feedback group report severe symptoms, the care team will receive an alert but as noted above, alerts to the clinical team can only be monitored during business hours, so all patients must seek care after hours in the current standard care fashion.

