### Study outcomes

	Aims	Measure	Data Source(s)	Assessment Time Point
Patient-Centered Outcomes	SA1			
Emergency Department Visits	SA1a	UCC visit at MSKCC	MSK institutional database	Up to 30 days after surgery
	SA1a	Emergency department visit outside MSKCC	Patient self-reporting via Patient Portal and corroborating phone call to patient by study team; MSK institutional database	Up to 30 days after surgery
Readmissions	SA1a	Readmission to MSK	MSK institutional database	Up to 30 days after surgery
	SA1a	Admission outside MSK	Patient self-reporting via Patient Portal and corroborating phone call to patient by study team; MSK institutional database	Up to 30 days after surgery
Symptom-Triggered Interventions	SA1b	Nurse calls due to alerts	Documented in EMR via clinical information system	Up to 30 days after surgery
	SA1b	Unplanned clinic visits and phone referral to clinic	Documented in EMR	Up to 30 days after surgery

	SA1b	Pain management referrals	Documented in EMR	Up to 30 days after surgery
	SA1b	Adverse event detection	EMR and MSKCC Surgical Secondary Events Database	Up to 30 days after surgery
Patient and Caregiver Health Care Experience	SA2			
Patient Engagement	SA2a	The Patient Activation Measure 	Patient self-report	Preoperatively (day of consent-POD1), 2 weeks (+7/-3 days), 60 (+/- 14) days after surgery
	SA2a	Qualitative data	Semistructured patient interviews	30 (+/- 10) days after surgery
Patient Anxiety	SA2b	PRO-CTCAE Anxiety Items	Patient self-report via symptom monitoring module in the Patient Portal	Daily for 10 days after surgery
Caregiver Burden	SA2c	Caregiver Reaction Assessment 	Caregiver self-report	2 weeks (+7/-3 days), 60 (+/- 14) days after surgery
	SA2c	Qualitative data	Semistructured caregiver interviews	30 (+/- 10) days after surgery

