### Power calculation

Sample size and power calculations were based on the primary outcome, the difference in emergency department visits without admission, between the Enhanced Feedback and Team Monitoring arms. On the basis of current MSKCC data, we expect for every 1,000 eligible patients treated surgically at JRSC, 69 patients will make emergency department visits. We also estimate that of these 69 patients, 28 will require readmission, and hence 41 will have visits the emergency department unnecessarily. The majority of such unnecessary visits are related to concerns about symptoms, which might be avoided if patients have a better understanding of expected symptom severity. Using a traditional alpha of 5% and an event rate of 4.1% in the control group, the power to detect different relative risk reductions is given below for a total sample size of 2,750 patients.

Relative Risk Reduction	Power
33%	45%
40%	64%
50%	85%
67%	96%

The primary analysis will compare, between groups, the proportion of patients with at least 1 emergency department visit without admission within 30 days (SA1a) of surgery by logistic regression with randomization strata as covariates. A difference between proportions will be calculated along with a 95% CI by applying the odds ratio from the regression to the event rate in the control group. A similar statistical approach will be taken for the proportion of patients referred to pain management and unplanned clinic visits (SA1b). For nursing follow-up calls (SA1b), phone referrals (SA1b) and rates of adverse events (SA1b), we will use both a binary approach (e.g., at least 1 nursing call vs. no nursing call) and analysis of count data using negative binomial regression with randomization strata as covariates. For all binary endpoints, an event will be counted only if it occurs within 30 days of surgery.

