### **Data sources and data linkage plans**

Many of the study endpoints will be obtained from MSKCC's institutional database. Endpoints such as MSKCC emergency department visits, nursing follow-up calls, clinic visits, and intrainstitutional referrals are automatically captured as part of electronic medical record (EMR)-enabled care management. Emergency department visits at outside institutions will be captured by a question on our daily symptom surveys and routine follow-up surveys. Responses to the follow up surveys will be captured electronically via MSK Engage. Patients describing an emergency department visit at an institution other than MSKCC are contacted by clinical staff for further details as a routine part of follow-up care. Adverse events are captured by the MSKCC Secondary Surgical Event database. Outside emergency department visits and admissions for patients participating in MSKCC's electronic health information exchange will also be utilized. Electronic health information exchange is carried out through organizations known as Health Information Exchanges (HIEs) or Regional Health Information Organizations (RHIOs). This data is captured within MSKCC's institutional database. Data for all patients who choose to opt out of the health information exchange program will not be used. To note: MSK may join additional HIEs or RHIOs in the future. Any available HIE or RHIO data for participating patients will be collected. PROs are obtained through MSKCC's symptom monitoring software, the same software used to implement symptom self-reporting. Covariates such as age, sex, and race are routinely captured in the MSKCC EMR. Comorbidities are captured by an MSKCC platform used to take the baseline medical history in all surgical patients potentially eligible for ambulatory cancer surgery. Caregivers' responses to the Caregiver Reaction Assessment questionnaires will be

collected via REDCap, a secure web application for building and managing online surveys and databases. In the event the REDCap survey is unavailable, a hardcopy form will be provided to caregivers to complete.

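### A lower all-grade adverse event rate in Enhanced Feedback cannot by itself be read as fewer events, because events below the severe level may be recorded differently by arm

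*Combined protocol and SAP*

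**What the plan says.** Section 4.2 (Secondary outcomes, SA1) places detection among the symptom-triggered interventions and then names rates as a further outcome: "adverse event detection) and rates of adverse events up to 30 days after ambulatory cancer surgery". It adopts the institution's surgical secondary events grading system to define adverse events.

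The Study outcomes table in Section 4.3 has one adverse event row. It is labelled as detection, and its source is "EMR and MSKCC Surgical Secondary Events Database". Section 11.0 (Data sources and data linkage plans) says: "Adverse events are captured by the MSKCC Secondary Surgical Event database".

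The analysis text in Section 11.0 (under Power calculation) deals only with rates: "phone referrals (SA1b) and rates of adverse events (SA1b), we will use both a binary approach", together with negative binomial regression for counts. It plans no analysis by grade and no separate analysis of detection.

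Section 4.3 describes when the clinical team becomes involved in each arm.

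- Team Monitoring: "The care team is alerted when patients experience symptoms out of the expected range or if symptoms are worsening". In addition, "If a patient responds with a moderate-severe answer, the office team gets an alert and calls" the patient in business hours. The stated purpose is that "This platform promotes early detection and intervention".
- Enhanced Feedback: "when patients in the Enhanced Feedback group report severe symptoms, the care team will receive an alert". Otherwise the patient decides whether to call.

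**The concern.** An event enters the medical record or the secondary events database only if it comes to someone's notice and is written down. The randomised contrast changes how often clinical staff speak to patients whose symptoms are moderate or worsening but not severe. One count is thus asked to serve both as a measure of what was found and as a measure of what happened. The plan does not say which reading applies, or whether a higher count is favourable.

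Section 3.0 expects fewer serious adverse events with feedback. A lower all-grade rate in Enhanced Feedback would fit that hypothesis, and it could also arise from recording alone. The plan has no check for this. The sensitivity analyses in Section 11.0 address unreported visits to outside emergency departments. The discussion of internal validity covers the primary endpoint and the advice nurses give. Section 12.3 states that the trial is unblinded, and no masked assessment of adverse events is described.

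**Working it through.** There is no plan figure to reproduce: the protocol gives no adverse event rate, detection probability or power for this outcome. The calculation below therefore shows only how a recording difference would carry through the planned analysis.

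**Inputs from the protocol.** 2,750 patients randomised 1:1, so n = 1,375 per arm; two-sided 5% test; negative binomial model for counts.

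**Assumptions (not in the protocol).**
- Equal true rates in both arms, with total rate t = 0.1, 0.2 or 0.3 events per patient.
- Dispersion 0.5.
- Half of the events are higher grade and always recorded in both arms.
- The other half are lower grade, recorded 95% of the time in Team Monitoring and a proportion d = 85% or 75% of the time in Enhanced Feedback.

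**Formulas.**
- Recorded rate, Team Monitoring: m_T = t × (0.5 + 0.5 × 0.95) = 0.975t
- Recorded rate, Enhanced Feedback: m_E = t × (0.5 + 0.5d)
- Apparent rate ratio: RR = m_E / m_T
- SE of log RR: √[(1/m_T + 0.5 + 1/m_E + 0.5) / 1,375]
- Chance of a significant result favouring Enhanced Feedback: Φ(|log RR| / SE − 1.96)

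**Rate ratio.** For d = 85%, 0.925 / 0.975 = 0.95. For d = 75%, 0.875 / 0.975 = 0.90.

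**One case in full (t = 0.2, d = 75%).** m_T = 0.195 and m_E = 0.175. log RR = −0.108. SE = √[(5.128 + 0.5 + 5.714 + 0.5) / 1,375] = 0.0928. The ratio of the two is 1.17 in absolute value, and Φ(1.17 − 1.96) = 21%.

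**Chance of a false significant benefit (2.5% with no recording difference):**

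| Total true rate | 95% v 85% (RR 0.95) | 95% v 75% (RR 0.90) |
|---|---|---|
| 0.1 | 6% | 13% |
| 0.2 | 8% | 21% |
| 0.3 | 10% | 29% |

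**A smaller gap across all events.** With 95% v 90% recording of every event, RR = 0.90 / 0.95 = 0.95 and the chance is 6%, 8% and 10% at the three rates. With 95% v 93%, it is 4–5%.

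**Binary version of the outcome.** With 90% v 85% recording of all affected patients, a two-proportion test with 1,375 per arm gives an observed ratio of 0.94. The chance is 5%, 7% and 10% at true proportions of 5%, 10% and 20%. The binary and count approaches are therefore exposed to a similar degree.

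**The case against.** The strongest reply is that this is loose labelling of a secondary outcome, and that the safeguards common to both arms are substantial. Both arms complete the same daily tracker. Section 4.3 describes responses flowing into the health record without distinguishing arms. Severe symptoms alert the team in both arms, and chart extraction for 30 days is planned for everyone. These points stand, and they confine the problem mainly to events below the severe level. They do not remove it, since chart extraction finds only what was documented.

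The direction is also open to challenge. The protocol nowhere says that nurse calls feed the secondary events database. Patients who see that their symptoms exceed the norm may call, and that generates entries too. Earlier contact in Team Monitoring could prevent events. Section 1.0 even describes Enhanced Feedback as including nursing outreach if indicated, whereas Sections 2.0 and 3.0 describe patient-activated care; those descriptions should be reconciled. This objection stands as far as certainty goes: the direction is plausible, not documented.

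A reader might infer three stronger conclusions that the documents do not support.

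- **A large false benefit is likely.** If every event is treated as lower grade (95% v 75–85% recorded, same rates and dispersion), the apparent ratio is 0.79–0.89 and the chance of a false benefit is 13–83%. But the planned comparison covers all events, and higher-grade events that come to notice in both arms dilute the difference.
- **A rise in serious events would be hidden.** Severe-symptom alerts operate in both arms, and emergency department visits and readmissions, inside and outside the centre, are separate 30-day outcomes. An increase in events leading to admission should show there.
- **The investigators have committed to reporting a lower count as a safety gain.** No passage says so, and none assigns a favourable direction to detection. The plan leaves the interpretation open.

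**Conclusion.** The point holds in a limited form. The protocol names detection and rates together, draws them from overlapping records, analyses one all-event comparison, and randomises patients to different levels of clinician contact below the severe level. Occurrence and recording cannot be separated in that comparison, and nothing in the plan addresses it.

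The size is unknown. The illustrative range (rate ratio 0.90–0.95, chance of a false benefit 6–29%) rests entirely on the assumed rates, dispersion, half share of lower-grade events and recording probabilities. A gap of two percentage points would barely matter (4–5%). This is a minor matter of interpretation for a secondary outcome, and it does not touch the primary endpoint.

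**What to change.** In Section 11.0:

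1. Keep the all-grade comparison, but label it as occurrence plus detection, and state that it will not be interpreted as a safety benefit on its own.
2. Add a between-arm comparison by grade, using the grading system that Section 4.2 already adopts.
3. Base any statement about occurrence on the higher grades. Before any unblinded analysis, specify the grades judged unlikely to depend on nurse contact. A need for intervention is not a sufficient criterion, because contact can itself lead to intervention.
4. Read the higher-grade result alongside the planned readmission and emergency department outcomes.

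The cost is SAP wording and one extra table, with no new data collection. The higher-grade comparison will have fewer events and wider intervals, and it will overlap to some extent with readmissions. The primary analysis does not change.
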